**Table 9-6: Blood collection time points for PK analysis for Part B and Part C**

## **9.6 Efficacy assessments**

Planned time points for all tertiary/exploratory antitumor activity assessments are provided in the Schedules of Activities for Part A ([Table 1-4](#)), Part A1 ([Table 1-5 and Table 1-6](#)), Part B ([Table 1-7](#)), and Part C ([Table 1-8](#)). Primary, secondary, and tertiary/exploratory antitumor activity assessments for Parts A1, D, E, F, and G will be described in a protocol amendment.

### **9.6.1 Tumor assessments**

Tumor assessments will be performed as outlined in the Schedules of Activities for Part A ([Table 1-4](#)), Part A1 ([Table 1-5 and Table 1-6](#)), Part B ([Table 1-7](#)), and Part C ([Table 1-8](#)). The same imaging technique used to characterize each identified and reported lesion at Baseline will be employed in subsequent tumor assessments.

Screening tumor assessments must be performed within 42 days prior to the first dose of UCB6114, and include at a minimum a computed tomography (CT) or magnetic resonance imaging (MRI) scan of the chest, abdomen, and pelvis (if relevant), and any other areas of known or suspected disease. A CT or MRI scan that is dated prior to consent for this study may be used as the Screening assessment, where this has been performed as per standard care or at the end of a prior research study

Thereafter, tumor assessments of the chest, abdomen, and pelvis (if applicable) and any other areas of disease found at Screening, or newly suspected at follow-up, are to be performed

between Days 21 and 28 of every even-numbered cycle and at the SFU Visit unless the participant has already withdrawn due to progressive disease or if the previous tumor assessment was within 6 weeks of SFU Visit.

Bone lesions can be assessed with CT and MRI. Further tests may be required for assessing bone lesions and they will be performed at the investigator's discretion and per clinical practice.

The method of tumor assessment should follow the RECIST (Version 1.1) criteria detailed in Appendix 9 (Section 11.9). If subcutaneous masses or nodes are palpable (eg, bulky) and are assessable by both clinical and radiographic techniques, the radiographic (CT/MRI) technique should be used for the assessment of target and non-target lesions. Assessment is to be performed at the site by appropriately qualified personnel (radiologist and clinical investigator) and results are to be recorded in the eCRF.

In the event of CR or PR, the tumor assessment should be confirmed. The confirmation assessment is done at least 4 weeks after the response is recorded, typically at the next scheduled assessment time point. If bone lesion assessments are a part of the tumor assessment, the bone assessments should be repeated at the time of the confirmation scan.

Any redacted scan data may be collected for verification/central reading.

### **9.6.2 ECOG Performance Status**

Measures of ECOG Performance Status will be taken at visits outlined in the Schedules of Activities for Part A (Table 1-4), Part A1 (Table 1-5 and Table 1-6), Part B (Table 1-7), and Part C (Table 1-8). ECOG Performance Status will be determined according to the table provided in Appendix 8 (Section 11.8).

### **9.7 Genetics**

Planned time points for all genetic assessments are provided in the Schedules of Activities for Part A (Table 1-4), Part A1 (Table 1-5 and Table 1-6), Part B (Table 1-7), and Part C (Table 1-8). Genetic assessments for Parts A1, D, E, F, and G will be defined in a protocol amendment.

Where local regulation and IEC allow, an 8.5mL blood sample for deoxyribonucleic acid (DNA) isolation will be collected from participants and may be used to perform genetic analysis to help understand a participant's response to UCB6114.

See Appendix 5 (Section 11.5) for information regarding genetic research. Details on processes for collection and shipment of these samples can be found in the laboratory manual.

### **9.8 Pharmacodynamics**

Planned time points for all tertiary/exploratory PD assessments are provided in the Schedules of Activities for Part A (Table 1-4), Part A1 (Table 1-5 and Table 1-6), Part B (Table 1-7), and Part C (Table 1-8). All tertiary/exploratory PD assessments for Parts D, E, F, and G will be defined in a protocol amendment.

Blood samples for PD analysis will be collected at the time points discussed in the following sections.

Blood samples of various volumes may be collected for analysis in a range of PD assays ([Table 9-1](#)). In Part A, the number of blood samples and total volume collected per cycle and at the SFU Visit will be as follows:

- In Cycle 1, up to 12 blood samples totaling approximately 83.5mL
- In Cycle 2, up to 5 blood samples totaling approximately 35.5mL
- In Cycle 3, up to 5 blood samples totaling approximately 35.5mL
- In Cycle 4, up to 4 blood samples totaling approximately 15.5mL
- At the SFU Visit, up to 5 blood samples totaling approximately 35.5mL

In Part A1, the number of blood samples and total volume collected per cycle and at the SFU Visit will be as follows:

- In Screening, up to 4 blood samples totaling approximately 36 mL in each Cohort
- Cycle 1, up to 7 blood samples totaling approximately 43.5mL in Cohorts 1, 2, 4 and up to 4 blood samples totaling approximately 16mL in Cohort 3
- In Cycle 2, up to 4 blood samples totaling approximately 31.5mL in each Cohort
- In Cycle 3 up to 5 blood samples totaling approximately 35.5mL in each Cohort
- From Cycle 4 onwards and at the SFU Visit up to 4 blood samples totaling approximately 31.5mL in each Cohort

One additional sample for circulating gremlin-1 (4mL) may be taken on the day of the on-treatment biopsy if taking place on a day where no circulating gremlin-1 sample is scheduled.

In Parts B and C, the number of blood samples and total volume collected per cycle and at the SFU Visit will be as follows:

- In Screening, up to 3 blood samples totaling approximately 32.5mL
- In Cycle 1, up to 4 blood samples totaling approximately 32mL
- In Cycle 2, up to 6 blood samples totaling approximately 56mL
- From Cycle 3 onwards, up to 3 blood samples totaling approximately 28mL
- At the SFU Visit, up to 3 blood samples totaling approximately 28mL

Tumor biopsies will also be collected during the study (see Section [9.8.7](#)).

### **9.8.1 Blood samples for circulating gremlin-1**

Whole blood samples of approximately 4mL per time point will be collected and processed to serum for measurement of total circulating gremlin-1 levels. Sampling time points throughout the study are outlined in the Schedules of Activities for Part A ([Table 1-4](#)), Part A1 ([Table 1-5](#) and [Table 1-6](#)), Part B ([Table 1-7](#)), and Part C ([Table 1-8](#)). Sampling collection times relative to dosing are detailed in [Table 9-7](#) (Part A), in [Table 9-8](#) (Part A1) and [Table 9-9](#) (Part B and Part C).

Instructions pertaining to sample collection, processing, storage, labeling, and shipping are provided in the laboratory manual for this study.

**Table 9-7: Sample time points for serum gremlin-1 analysis in Part A**

Cycle	Day	Sampling time relative to dosing	Sampling time
Cycle 1	Day 1	Baseline	Predose
	Day 2	+24h	Postdose on Cycle 1 Day 1
	Day 15	Within 0.5h prior to dosing	Predose
Subsequent cycles (up to and including Cycle 4)	Day 1	Within 0.5h prior to dosing	Predose
SFU Visit	On day of visit	On day of visit	NA

h=hour; NA=not applicable; SFU=Safety Follow-Up

Note: The time window for blood sample collection at the 24h PD time point postdose (Cycle Day 2) is  $\pm$  0.5h.

**Table 9-8: Sample time points for serum gremlin-1 analysis in Part A1**

Cycle a	Day	Sampling time relative to dosing	Sampling time
Cycle 1	Day 1	Baseline	Predose
	Day 1	End of infusion (+15min)	Postdose
	Day 1	+4h (+1h)	Postdose
	Day 15 b	Within 0.5h prior to dosing/day of visit	Predose/NA
Cycle 2	Day 1	Within 0.5h prior to dosing	Predose
Cycle 3	Day 1	Within 0.5h prior to dosing	Predose
	Day 1	+4h (+1h)	Postdose
Cycle 4 onwards	Day 1	Baseline	Predose
SFU Visit	On day of visit	On day of visit	NA

a An additional sample should also be collected on the day of the on-treatment biopsy (only if taking place on a day where no serum gremlin-1 samples are scheduled)

b Predose for a 2-weekly cycle (Cohorts 1 and 2) but on day of visit for a 3-weekly or a 4-weekly cycle (Cohorts 3 and 4)

h=hour; NA=not applicable; SFU=Safety Follow-Up

**Table 9-9: Sample time points for serum gremlin-1 analysis in Part B and Part C**

Cycle	Day	Sampling time relative to dosing with UCB6114	Sampling time
Screening	Once between Day -28 and -1	NA	NA
Cycle 1	Day 15	Within 0.5h prior to dosing	Predose
Cycle 2	Day 1	Within 0.5h prior to dosing	Predose
	Day 15	Within 0.5h prior to dosing	Predose
Cycle 3 (onward) a	Day 1	Within 0.5h prior to dosing	Predose
SFU Visit	On day of visit	On day of visit	NA

h=hour; NA=not applicable; SFU=Safety Follow-Up

a To be completed in cycle 3 and thereafter in even cycles only (ie, Cycle 4, 6)**9.8.2 Blood samples for serum protein analysis and blood transcriptomics**

In Part A and Part A1, whole blood samples of approximately 5mL per time point will be collected and processed to serum for analysis of protein markers. An additional whole blood sample of 2.5mL per time point may also be collected for potential transcriptomic analysis. Samples for analysis of protein markers or potential transcriptomic analysis will not be obtained in Part B or Part C.

Sampling time points for these assays are detailed in [Table 9-10](#) (Part A) and [Table 9-11](#) (Part A1).

Instructions pertaining to sample collection, processing, storage, labeling, and shipping are provided in the laboratory manual for this study.

**Table 9-10: Sample time points for serum protein analysis and blood transcriptomics in Part A**

Cycle	Day	Sampling time relative to dosing	Sampling time
Cycle 1	Day 1	Baseline	Predose
	Day 15	Within 0.5h prior to dosing	Predose
Subsequent cycles (up to and including Cycle 4)	Day 1	Within 0.5h prior to dosing	Predose
SFU Visit	On day of visit	On day of visit	NA

h=hour; NA=not applicable; SFU=Safety Follow-Up

**Table 9-11: Sample time points for serum protein analysis and blood transcriptomics in Part A1**

Cycle	Day	Sampling time relative to dosing	Sampling time
2-weekly and 4-weekly cycles (Cohorts 1, 2 and 4)			
Screening	Day-14 to -1	Baseline	
Cycle 1	Day 15	Within 0.5h prior to dosing (Cohorts 1 and 2)/on day of visit (Cohort 4)	Predose(Cohorts 1 and 2)/ NA (Cohort 4)
Subsequent cycles	Day 1	Within 0.5h prior to dosing	Predose
SFU Visit	On day of visit	On day of visit	NA
3-weekly cycles (Cohort 3)			
Screening	Day-14 to -1	Baseline	
Cycle 2 onwards	Day 1	Within 0.5h prior to dosing	Predose
SFU Visit	On day of visit	On day of visit	NA

h=hour; NA=not applicable; SFU=Safety Follow-Up

### 9.8.3 Blood samples for circulating tumor DNA analysis

Whole blood samples of approximately 20mL per time point will be collected and processed for analysis of circulating tumor DNA (ctDNA).

Sampling time points are detailed in [Table 9-12](#) (Part A), [Table 9-13](#) (Part A1) and [Table 9-14](#) (Part B and Part C).

Instructions pertaining to sample collection, processing, storage, labeling, and shipping are provided in the laboratory manual for this study.

**Table 9-12: Sample time points for ctDNA analysis in Part A**

Cycle	Day	Sampling time relative to dosing	Sampling time
Cycle 1	Day 1	Baseline	Predose
	Day 15	Within 0.5h prior to dosing	Predose
Subsequent cycles (up to and including Cycle 3)	Day 1	Within 0.5h prior to dosing	Predose
SFU Visit	On day of visit	On day of visit	NA

ctDNA=circulating tumor DNA; h=hour; NA=not applicable; SFU=Safety Follow-Up

**Table 9-13: Sample time points for ctDNA analysis in Part A1**

Cycle	Day	Sampling time relative to dosing	Sampling time
2-weekly and 4-weekly cycles (Cohorts 1, 2 and 4)			
Screening	Day-14 to -1	Baseline	
Cycle 1	Day 15	Within 0.5h prior to dosing (Cohorts 1 and 2)/on day of visit (Cohort 4)	Predose(Cohorts 1 and 2)/ NA (Cohort 4)
Subsequent cycles	Day 1	Within 0.5h prior to dosing	Predose
SFU Visit	On day of visit	On day of visit	NA
3-weekly cycles (Cohort 3)			
Screening	Day-14 to -1	Baseline	
Cycle 2 onwards	Day 1	Within 0.5h prior to dosing	Predose
SFU Visit	On day of visit	On day of visit	NA

h=hour; NA=not applicable; SFU=Safety Follow-Up

**Table 9-14: Sample time points for ctDNA analysis in Part B and Part C**

Cycle	Day	Sampling time relative to dosing with UCB6114	Sampling time
Screening	Once between Day -28 and -1	NA	NA
Cycle 1	Day 15	Within 0.5h prior to dosing	Predose
Cycle 2	Day 1	Within 0.5h prior to dosing	Predose
	Day 15	Within 0.5h prior to dosing	Predose
Cycle 3 (onward)	Day 1	Within 0.5h prior to dosing	Predose
SFU Visit	On day of visit	On day of visit	NA

ctDNA=circulating tumor DNA; h=hour; NA=not applicable; SFU=Safety Follow-Up

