**Table 1-7: Schedule of Activities for Part B**

Procedure	Screening		Treatment						SFU Visit Within 30 days after final dose	Final Visit 3 months after final dose
	-28 to -1	-3 to -1	Cycle 1 & Cycle 2 (28 days)			Cycle 3 onwards (28 days)				
Cycle day	1	8	15	22	1	15				

f A complete physical examination is to be performed in Screening and does not have to be repeated on Day 1 pre-dose if performed within 3 days prior to starting any IMP. Physical examinations will be symptom-directed and performed prior to administration of IMP on all other visits.

g Not to be done in Cycle 2.

h Vital signs and ECOG performance status are to be performed in Screening and do not have to be repeated on Day 1 pre-dose if performed within 3 days prior to starting any IMP. Vital signs on treatment days with UCB6114 will be assessed at multiple time points in a semi-supine position after 5min of rest: pre-dose, 10min ( $\pm$ 5min) and 30min ( $\pm$ 10min) after the start of the infusion, at the end of the infusion (+15min); and at 1h (+15min) after the end of the infusion. In addition, on Cycle 1 Day 1 vital signs will be assessed at 2h (+1h) and 5h (+1h) after the end of the infusion.

i Urinalysis is to be performed in Screening and does not have to be repeated on Day 1 pre-dose if performed within 3 days prior to starting any IMP. If there are abnormalities in urine dipstick, a microscopic analysis should be performed (including crystals).

j Deleted

k Hematology is to be performed in Screening and does not have to be repeated on Day 1 pre-dose if performed within 3 days prior to starting any IMP. At all other visits, the hematology sample may be obtained 24h prior to the scheduled visit.

l Blood chemistry is to be performed in Screening and does not have to be repeated on Day 1 if performed within 3 days prior to dosing with any IMP. At all other visits blood, the chemistry sample may be obtained 24h prior to the scheduled visit. In the case of liver function abnormalities considered potential Hy's law cases, the liver-specific ALP must be separated from the total in participants with bone metastases and used to assess the liver function instead of the total ALP.

m Coagulation is to be performed in Screening and does not have to be repeated on Day 1 pre-dose if performed within 3 days prior to starting any IMP. At all

o No sample required if done previously.

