**Table 3-2: Objectives and endpoints for the dose escalation modules in Part B and Part C**

Objectives	Endpoints
Primary	
To characterize the safety profile of UCB6114 administered in combination with selected SOC regimens	Incidence of TEAEs Severity of TEAEs Incidence of DLTs
Secondary	
To characterize the PK of UCB6114 administered in combination with selected SOC regimens	UCB6114 concentration by scheduled assessment and dose level
Tertiary/exploratory	
To document any antitumor activity observed with UCB6114 administered in combination with selected SOC regimens according to relevant RECIST criteria	Antitumor activity as indicated by: 

• ORR

• DCR

• DOR

• PFS

• OS

To explore PD biomarkers of UCB6114 administered in combination with selected SOC regimens	

• Change in protein marker levels in blood by scheduled assessment and dose level

• Change in ctDNA levels in blood by scheduled assessment and dose level

To evaluate the immunogenicity of UCB6114 administered in combination with selected SOC regimens	ADA (anti-UCB6114 antibody) titer and sample status by scheduled assessment

ADA=antidrug antibody; ctDNA=circulating tumor DNA; DCR=disease control rate; DLT=dose-limiting toxicity; DOR=duration of antitumor response; ORR=objective response rate; OS=overall survival; PD=pharmacodynamic(s); PFS=progression-free survival; PK=pharmacokinetic(s); RECIST=Response Evaluation Criteria in Solid Tumors; SOC=standard of care; TEAE=treatment-emergent adverse event

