## Type of participant and disease characteristics

2. Participant has a histologically and/or cytologically confirmed diagnosis of one of the following advanced solid tumor types: colorectal adenocarcinoma, gastric adenocarcinoma, or adenocarcinoma of the gastroesophageal junction.
- 3a. Participant has advanced disease (ie, unresectable locally advanced or metastatic).
- 4a. Participants must have received, or be intolerant to, or deemed not suitable for, at least 2 prior regimens of treatment, including the following standard of care anti-cancer treatments (where such treatments are available as standard of care):
  - a. Participants with colorectal cancer: fluoropyrimidine-, oxaliplatin-, and irinotecan-based chemotherapy, an anti-vascular endothelial growth factor biological therapy, and, if RAS wild-type, an anti-epidermal growth factor receptor (EGFR) therapy, or if microsatellite instability high/deficient mismatch repair (MSI-H/dMMR) immunotherapy (eg, nivolumab, pembrolizumab and ipilimumab).
  - b. Participants with gastric or gastroesophageal junction adenocarcinoma: fluoropyrimidine, a platinum, either a taxane or irinotecan, ramucirumab, and, if appropriate, human EGFR 2/neu-targeted therapy.
5. Participant has measurable or nonmeasurable disease as defined by the relevant RECIST.
6. Participant has a performance status of  $\leq 1$  on the ECOG scale.
7. Participant has discontinued all previous therapies for cancer (with exception of treatments defined in Section 6.5.3 ), including chemotherapy, radiotherapy, cancer-related hormonal therapy, or other investigational therapy for a minimum of 28 days or 5 half-lives (whichever is shorter) (6 weeks for mitomycin-C or nitrosoureas) prior to start of study medication and recovered from the acute effects of therapy.  
Any clinically significant treatment-related toxicity from prior therapy must have resolved to Grade  $\leq 1$  prior to study entry, with the exception of alopecia.
8. Participant has an estimated life expectancy of  $\geq 12$  weeks.

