#### **9.8.4 Blood samples for serum bone turnover markers**

In Parts A, B, and C, whole blood samples of approximately 4mL per time point will be collected and processed to serum for analysis of circulating markers of bone turnover. Sampling time points throughout the study are outlined in the Schedules of Activities for Part A (Table 1-4), Part B (Table 1-7), and Part C (Table 1-8).

Sampling collection time points relative to dosing are detailed for Part A in Table 9-15 and for Parts B and C in Table 9-16.

Instructions pertaining to sample collection processing, storage, labeling, and shipping are provided in the laboratory manual for this study.

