## 10.2 General statistical considerations

All analyses will be performed using SAS® Version 9.2 or higher (SAS Institute, Cary, NC, US).

Descriptive statistics will be used to provide an overview of the Baseline, safety, PK, PD, and other exploratory results. For categorical and ordinal variables, the number and percentage of participants in each category will be presented. The denominator for the percentages will be based on the number of participants appropriate for the purpose of analysis. Unless otherwise noted, all percentages will be expressed to 1 decimal place. For continuous variables, descriptive statistics will include, but will not be limited to, the number of participants, mean, median, standard deviation, minimum, and maximum.

Definitions of Baseline for each variable, as applicable, will be included in the SAPs for each module.

No formal hypothesis testing will be performed in Part A, Part A1, Part B or Part C.

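### In Parts B and C the only pre-treatment ctDNA and gremlin-1 sample can predate first dosing by up to 28 days, adding avoidable noise to the exploratory change summaries

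*Protocol*

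**What the plan says.** Table 3-2 of the Protocol lists, among the tertiary/exploratory endpoints for Parts B and C, "Change in ctDNA levels in blood by scheduled assessment and dose level". Change in blood protein markers stands beside it.

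Tables 9-9 (gremlin-1) and 9-14 (ctDNA) each give one pre-treatment sample, timed "Once between Day -28 and -1". The next row in both tables is Cycle 1 Day 15. Tables 1-7 and 1-8 also mark a second screening column (Day -3 to -1 in Part B, Day -14 to -1 in Part C) and Day 1, but attach footnote o to both: "No sample required if done previously".

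Inclusion criterion 7 of Sections 5.1.3 and 5.1.4 requires prior cancer therapy to have been stopped "for a minimum of 28 days or 5 half-lives (whichever is shorter) (6 weeks for mitomycin-C or nitrosoureas) prior to start of study medication". The sample date plays no part in that rule.

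Elsewhere the Protocol takes comparable baselines just before dosing. In Part A both ctDNA and gremlin-1 are sampled predose on Cycle 1 Day 1 (Tables 9-7 and 9-12). In Parts B and C the bone turnover markers have a Cycle 1 Day 1 predose Baseline row (Table 9-16). No reason is given for the wider window for ctDNA and gremlin-1.

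**The concern.** A change from pre-treatment is easiest to read when the reference sample is taken just before the first dose. Here a Day -28 draw can be the only pre-dose value. The later change then includes up to four weeks with no study treatment, and possibly the tail of the previous regimen. The amount depends on when each participant was screened and what they last received, so it differs from one participant to the next.

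The summaries affected are by dose level, with 3 to 9 participants per level (Sections 4.1.4.2.2 and 4.1.5.2.2). Groups that small cannot average out such variation. PD biomarkers are one of the inputs to the recommended combination doses (Sections 4.1.4.3 and 4.1.5.3).

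Section 10.2 says "Definitions of Baseline for each variable, as applicable, will be included in the SAPs for each module", so the choice of reference value is properly left to the SAP. But an SAP can only choose among samples that were drawn.

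**Working it through.** **1. Is a Day 1 ctDNA or gremlin-1 sample planned?** The Part B/C blood volumes in Section 9.8 answer this. Inputs per sample: ctDNA 20mL (Section 9.8.3), gremlin-1 4mL (9.8.1), serum bone markers 4mL (9.8.4), genetic sample 8.5mL (9.8.6).

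- Screening: 20 + 4 + 8.5 = 32.5mL, 3 samples. Stated: 32.5mL, 3 samples.
- Cycle 1: bone markers 4 (Day 1) + 4 (Day 15) + gremlin-1 4 (Day 15) + ctDNA 20 (Day 15) = 32mL, 4 samples. Stated: 32mL, 4 samples.
- Cycle 2: 2 × (4 + 4 + 20) = 56mL, 6 samples. Stated: 56mL, 6 samples.

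All three figures are reproduced. The Cycle 1 figure matches only with no ctDNA or gremlin-1 tube on Day 1, so the screening draw is the planned reference.

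**2. Interval to the first on-treatment sample** (nominal days, no Day 0, ignoring the visit window). Day 15 is 14 days after Day 1.

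- Draw on Day -28: 28 + 14 = 42 days, of which 28/42 = 67% precede treatment.
- Draw on Day -1: 1 + 14 = 15 days, of which 1/15 = 7% precede treatment.
- Draw on Day 1 predose: 14 days, all on treatment.

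**3. Overlap with washout.** Five half-lives is shorter than 28 days when the half-life is below 28/5 = 5.6 days. For a 1-day half-life, criterion 7 alone would allow a last prior dose on Day -5, which is 28 − 5 = 23 days after a Day -28 sample. Exclusion criterion 21 in each part refers to prohibited medication within 28 days and could be read more strictly. Even under a flat 28-day rule, a Day -28 sample can fall at the end of prior therapy.

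**4. Illustrative size of drift, ctDNA only.** The Protocol gives no growth rate, so the doubling time T is assumed to be 30 to 90 days. Drift over 28 days is 2^(28/T). A true halving from the Day 1 level reads as 0.5 × 2^(28/T) relative to a Day -28 sample.

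| T (days) | Drift over 28 days | True −50% reads as |
|---|---|---|
| 30 | 1.91-fold | 0.5 × 1.91 = 0.955, about −5% |
| 60 | 1.38-fold | 0.5 × 1.382 = 0.691, about −31% |
| 90 | 1.24-fold | 0.5 × 1.241 = 0.62, about −38% |

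With a Day -1 draw the corresponding drift is 2^(1/30) = 1.02-fold or 2^(1/90) = 1.01-fold, which is negligible.

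**The case against.** The strongest reply is about weight. These endpoints are exploratory, no hypothesis is tested in Parts A to C (Section 10.2), and PD results are descriptive and reported outside the main study report (Section 10.3.3.3). Escalation is guided by DLT counts under the mTPI scheme, not by ctDNA. All of that stands and limits the point to a cheap improvement.

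The drift figures are also a worst case on an assumed input. Sites may draw nearer to dosing, and Tables 1-7 and 1-8 permit Day 1 itself. No drift figure can be offered for gremlin-1. Comparisons among on-treatment samples are unaffected, although they do not give change from pre-treatment. The Protocol accepts a baseline scan up to 42 days before dosing (Section 9.6.1), so a 28-day window is not unusual within it. A blood draw, however, is far easier to move than a scan.

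A reader might infer more than the document supports:

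- *Bias between dose levels.* Nothing ties screening date or washout length to the assigned dose level. What follows is extra variation.
- *Isolation of the UCB6114 effect, or comparability with Part A.* Parts B and C are single-arm combinations with full-dose chemotherapy, and Part A is monotherapy in a wider range of tumors. A Day 1 sample would deliver neither.
- *All protein markers.* Bone markers already have a Day 1 baseline. Section 9.8.2 says protein-marker samples are not obtained in Parts B and C, so placing gremlin-1 under that endpoint is itself an inference.
- *The same change in Part A1.* Its ctDNA window is Day -14 to -1 and labelled Baseline, and its gremlin-1 is already predose on Day 1. The case there is weak.

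**Conclusion.** The point holds for ctDNA and circulating gremlin-1 in Parts B and C. The plan lets the only pre-dose value sit anywhere from 1 to 28 days before treatment, and the blood volumes confirm that no Day 1 sample is budgeted. A Day 1 value that was not drawn cannot be recovered by the SAP.

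The consequence is mainly added noise in exploratory summaries of 3 to 9 participants per dose level. For ctDNA the worst case is 1.24- to 1.91-fold drift, resting on the assumed 90- to 30-day doubling time and a Day -28 draw. No primary, secondary or escalation result depends on it. It merits changing because the change is cheap and matches the Protocol's own practice for other markers.

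**What to change.** In Tables 1-7, 1-8, 9-9 and 9-14, require the pre-treatment ctDNA and gremlin-1 sample on Cycle 1 Day 1 before any IMP. In Part B also allow Day -3 to -1, because TFD/TPI may be taken at home on Day 1, before the infusion visit. Remove footnote o from these two rows at that time point. The genetic sample can stay at Screening, and Part A1 needs no change.

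This also reconciles Tables 9-9 and 9-14, whose window ends at Day -1, with Tables 1-7 and 1-8, which allow a Day 1 draw.

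Cost: 20 + 4 = 24mL moves from Screening to Cycle 1, with no net increase in blood. For samples drawn on Day 1, Cycle 1 PD blood goes from 32 to 32 + 24 = 56mL and the Table 9-3 total from 77 to 77 + 24 = 101mL. Both equal the volumes already stated for Cycle 2. Screening PD blood falls from 32.5 to 8.5mL, and the volume statements in Sections 9 and 9.8 need matching edits.
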